1.1 Background

The PERDIEM study is a randomized trial comparing 30-day external loop recording cardiac rhythm monitoring to implantable loop recorder for 1-year, for stroke patients. The study included stroke patients with various mechanisms of stroke. The study is conducted in Calgary (1 tertiary site) and Edmonton (1 tertiary, 1 community site). The planned sample size is 300 patients.

1.2 Primary Objectives

The implantable loop recorder (ILR) plus remote monitoring will diagnose more paroxysmal AF / atrial flutter and provide better assessment of the total burden of AF resulting in a greater proportion of patients started on an OAC  versus the external loop recorder (ELR) strategy.

1.3 Study Design

Randomized, open label trial comparing two different extended ECG monitoring strategies for the detection of paroxysmal AF / atrial flutter after ischemic stroke or transient ischemic attack (TIA).

Inclusion Criteria:

1. Informed consent from the patient
2. Age \geq 18 years
3. Diagnosis of the index event* made by a stroke specialist of an acute ischemic stroke or TIA occurring within the last 6 months. The event must be either:
 - i) arterial ischemic stroke confirmed by neuroimaging; or ii) transient ischemic attack with DWI positive lesion on MRI
4. The patient is expected to survive at least 6 months
5. At least one 12-lead ECG has already been obtained as part of the routine clinical post-stroke/TIA work-up, and no ECGs have shown any episodes of atrial fibrillation or atrial flutter

6. The patient is being actively investigated for the etiology of the stroke/TIA event and additional cardiac monitoring is desired to screen further for the possibility of occult paroxysmal atrial fibrillation/flutter

Exclusion Criteria:

1. Previously documented atrial fibrillation/flutter.
2. Planned carotid endarterectomy or carotid artery stenting within 90 days.
3. Any condition for which there is already an indication for long term OAC.
4. Pacemaker or ICD device that would allow for detection of AF / atrial flutter.
5. Work-up for stroke that has already included extended (>7 days) external ECG.
6. Stroke and/or comorbid illness will prevent completion of planned follow-up assessments.

1.4 Sample Size Determination

A total of 300 patients will be randomized. This sample size reflects 8% inflation for cross over (2% with either strategy) and loss to follow-up (5% in each group). This sample size provides 85% power to assess a clear difference in rates of atrial arrhythmia (AF / atrial flutter) that results in initiation of additional anti-platelet or OAC therapy between the two strategies (two- sided alpha of 5%). This estimate is based on the following assumptions:

1. Equal allocation (1:1) to ELR for 30 days vs. ILR plus remote monitoring for 12 months.
2. 10% rate of AF / atrial flutter that results in initiation of additional anti-platelet or OAC therapy in the ELR and 20% rate of this endpoint in the ILR plus remote monitoring group.

This estimate was derived using the Two Independent Proportions (Null Case) Power Analysis estimation method (PASS 2012).

Table 1. Schedule of Assessments

	Pre-study (routine clinical studies)	Baseline (Day 0)	Day 30 (± 1 week)	6 months (\pm 2 weeks)	12 months +/- 4 weeks (telephone)	24 month +/-4 weeks (telephone)
Holter (optional)	X	Reports collected				
Echo (optional)	X	Reports collected				
Neuroimaging (CT or MRI)	X	Reports collected				
Vascular Imaging (CTA/MRA/doppler)	X	Reports collected				
ECG	X	Reports collected	X	X		
Informed consent, randomization		X				
Demographics		X				
Medical History		X			X	X
Vital signs	X*		X	X		
Antithrombotic and thrombolytic therapy		X	X	X	X	X
NIHSS		X				
CHA2DS2-VASc		X				
Stroke Subtype / Etiology (OCSS/TOAST)		X	X	X	X	X
Modified Rankin		X		X		
EQ-5D		X		X		
Adverse event assessment		X	X	X	X	X
New stroke/TIA, cardiac events		X	X	X	X	X
Return monitor / compliance diary			X			

1.5 Blinding

The study is conducted in an open-label non-blinded manner.

1.6 Definitions

Baseline: A subject's baseline value for a given endpoint or parameter is defined as his/her latest measurement taken prior to randomization.

Prior and Concomitant Medications: Prior medications are defined as those taken within three days of treatment initiation. Concomitant medications are defined as those taken during study follow-up. All prior and all concomitant medications will be recorded on the electronic case report form (e-CRF).

2.0 ANALYSIS POPULATIONS**2.1 Intent-to-Treat Population**

The study will be analysed by intention to treat (intention to monitor, in this case).

2.2 Per Protocol (PP) Population

The PP population will include all patients who underwent monitoring according to protocol and completed at least 1 month of follow-up.

3.0 INTERIM ANALYSES

There will be no interim analysis.

4.0 MISSING DATA AND DATA TRANSFORMATION

All efforts will be undertaken to avoid missing data. No planned imputation will be undertaken.

5.0 STATISTICAL METHODS

The software used for all summary statistical analyses will be STATA v16.1.

Percentages will be rounded to one decimal place, except 0% and 100% will be displayed without any decimal places. Minima and maxima will be rounded to the precision of the original value; means and medians will be rounded to one decimal place greater than the precision of the original value; SDs will be rounded to two decimal places greater than the precision of the original value. P-values will be reported to four decimal places (0.xxxx), with values less than 0.0001 presented as <0.0001.

Inferential analyses will generally include statistics such as 2-sided 95% confidence intervals (CI), and p-values. Unless stated otherwise, all statistical tests will be 2-sided Subject Disposition.

The primary outcome (atrial fibrillation) and the first composite secondary outcome (atrial fibrillation or death) will be analysed by intention to treat, using time-to-event analysis. Secondary outcomes will be reported as proportions.

5.1 Protocol Deviations and Protocol Violations

5.2 Demographic and Baseline Characteristics

Subject demographic and baseline characteristics will be summarized with descriptive statistics for each treatment group. Demographic variables include, but are not limited to: age, sex, race-ethnicity, weight as determined in hospital (in kg). Baseline characteristics include but are not limited to: prior use of alteplase (tPA), intended first thrombectomy approach (stent retriever or thrombus aspiration

6.0 EFFICACY ANALYSIS

6.1.1 Primary Outcome

The primary outcome will be the rate of detection of an atrial arrhythmia (AF / atrial flutter) that results in initiation of additional anti-platelet or OAC therapy as per usual clinical practice.

The first secondary outcome will be the composite of detection of an atrial arrhythmia (AF / atrial flutter) that results in initiation of additional anti-platelet or OAC therapy as per usual clinical practice or death (whichever occurs first).

Secondary Outcomes:

1. Recruitment rates.
2. Compliance with assigned therapy (accept ILR, conduct at least 80% of ELR assessments)
3. Time to detection of first episode of atrial fibrillation / atrial flutter \geq 30 seconds.
4. Costs for all cardiac and non-cardiac investigations related to etiologic workup of index stroke / TIA.

5. Total duration of any detected atrial fibrillation / atrial flutter.
6. Study related adverse events / serious adverse events.
7. Clinical recurrence of ischemic stroke / TIA, death, hemorrhagic stroke, major adverse bleeding, or death.
8. Relationship between duration detected AF and clinically silent strokes, volume of leukoaraiosis, numbers of cerebral microbleeds
9. Presence of cognitive impairment, progression of 12 months
Association between baseline clinical characteristics (e.g. comorbidities, burden of supraventricular ectopy on Holter, left atrial dimension) and subsequent detection of AF

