^a The decision to change the study endpoint to **definite AF lasting 2 minutes or more, including atrial flutter** was finalized by the steering committee on April 26, 2016, before the adjudication of any device data. The change was made due to technical limitations of the AF detection algorithm for the Medtronic LINQ implantable loop recorder studied. The shortest time over which the LINQ device can make a reliable assessment for AF is 2 minutes. The new endpoint was indicated in an adjudication document that was attached to the protocol

^b There was consensus from study investigators that 2 minutes or longer of **definite AF** in the setting of a recent stroke was likely to always be clinically actionable. The requirement for a change in antithrombotic medication was felt redundant and removed from the endpoint description.

List of Abbreviations

ADC	apparent diffusion coefficient
AF	atrial fibrillation
CRF	case report form
CT	computerized tomography
CTA	computerized tomography angiogram
DWI	diffusion-weighted imaging
ECG	electrocardiogram
ELR	external loop recorder
FLAIR	fluid-attenuated inversion recovery
GRE	gradient recalled echo
ICD	implantable cardiac defibrillator
ILR	implantable loop recorder
MRA	magnetic resonance angiogram
MRI	magnetic resonance imaging
OAC	oral anticoagulant
OCSP	Oxfordshire Classification of Stroke Program
REB	research ethics board
TIA	transient ischemic attack
TOAST	Test of Orgaran in Stroke Trial

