3.3 Study Enrollment Process

The study will be conducted over 24-30 months. A total of 300 patients will be recruited during from inpatient stroke units and stroke prevention clinics at the Foothills Medical Centre, University of Alberta Hospitals, and Grey Nuns Community Hospital using standard of care screening methods. Eligible patients will be randomized in a 1:1 ratio to receive either an ILR coupled with remote monitoring for 12 months versus an ELR for 30 days. A centralized web based randomization process will be used. Patients will be randomized in

small, variable block sizes. Both groups of patients will receive the best standard of care for secondary stroke prevention based on the Canadian best practices guidelines.(12)

Monitoring with ELR for 30 days

The ELR group will be fitted with a battery operated SpiderFlash-t (Sorin Group, USA) auto-triggered ELR and will be provided with a diary to track total hours worn per day and any clinical symptoms.

ILR with remote monitoring for 12 months

The ILR plus remote monitoring group will have a Health Canada approved Medtronic Reveal LINQ device surgically implanted. This is a miniaturized recorder about the size of a clip on a pen (44.8 mm x 7.2 mm x 4.0mm) (Figure 1a). It can be readily inserted in a procedure room with a very low risk of complications. It will be linked to a wireless (cellular) remote monitoring system (MyCareLink) (Figure 1b).

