- 4.0 Naming Convention will be for Calgary patients FMC-study number (delete clinic number 45 as this is misleading): For Edmonton patients GNH-study number (we need the site prefixes as the study numbers are randomized per site and not for the whole study)
- 5.0 The designated MD will have 2 business days to respond
- 6.0 If there is no response to the email, the ILR device nurse will send a reminder email
- 7.0 As soon as the response is received the ILR nurse will send report to the Study Coordinators with a copy to the PI ([name])

ILR Device Capabilities/Troubleshooting

1. Shortest duration of AF that Reveal LINQ can store is 2 minutes.
2. An "AF Alert" does not mean that the rhythm is definitely AF – this needs confirmed by a Cardiologist.
3. For PER DIEM the LINQ device is programmed to store AF Episodes with a duration of 2 minutes and longer. The nominal setting for Reason for Monitoring: Cryptogenic Stroke is "all episodes". Threshold Options are All Episodes, 6,10,20,60 minutes. For Cryptogenic stroke-use "all episodes".
4. When a patient is transferred from one clinic to another all of the device data is transferred. Care Alerts settings are not transferred from one clinic to another. They are set at the Root or Parent Clinic level. You can retrieve previous episodes by checking the episode tab.
5. The volume of Event Reports can be reduce by tailoring your Care Alerts to your patient population. You can reduce the duplication of episode review by marking the episode as reviewed under the Episode Tab.
6. If an Event Report for AF is received with "No Data Available" – please request that the patient send a manual transmission. This situation can occur with AF episodes <10 minutes in devices purchased prior to March 7, 2016.
7. You can reduce your false positives for under-sensing or over-sensing by reprogramming the LINQ device.

Please review the attached PDF file, indicate your responses below by marking with an "X" or highlighting the relevant answer and send your response within 2 business days of receipt to the sender.

1. Rhythm diagnosis (select one):

- No Atrial Fib/Aflutter
- Atrial Fib/Aflutter Possible
- Atrial Fib/Aflutter Definite/ High Probability

Identify event number(s) containing definite AF: _____

Duration of longest episode: _____

2. Other significant arrhythmia(s) (select all that apply):

- HR<40
- HR>140
- Sustained ventricular tachycardia / ventricular fibrillation
- Complete heart block
- Pause ≥5 s

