STATISTICAL ANALYSIS PLAN

Post-Embolic Rhythm Detection with Implantable versus External Monitoring (PER DIEM) Study

Feb 2019

Version 1.0

Trial Registration ClinicalTrials.gov Identifier: NCT02428140

Statistical Analysis Plan v1.0

Clarification Note:

The statistical analysis plan v1.0 (SAP) defines the primary outcome using the endpoint from the protocol version 4.0 (dated February 22, 2016). There was an additional amendment to the protocol on April 26, 2016, where the AF adjudication process was specified, and the primary endpoint was defined as **definite AF lasting 2 minutes or more, including atrial flutter**. Version 1.0 of the SAP incorrectly carried forward the primary endpoint based on the Feb 22, 2016 version 4.0 protocol rather than the updated definition of the primary endpoint as approved by the steering committee and amended to the protocol on April 26, 2016.

SIGNATURES OF APPROVAL

[name]., Principal Investigator
University of Alberta Hospital

March 1st, 2019

Date

[name]., Investigator
Director Stroke Unit, Foothills Medical Centre

1 Mar 2019

Date

TABLE OF CONTENTS

	Page
SIGNATURES OF APPROVAL.....	2
TABLE OF CONTENTS	3
LIST OF TABLES.....	4
LIST OF ABBREVIATIONS	5
1.0 INTRODUCTION.....	6
1.1 Background	6
1.2 Primary Objectives.....	6
1.3 Study Design	6
1.4 Sample Size Determination	7
Table 1. Schedule of Assessments.....	8
1.5 Blinding	9
1.6 Definitions.....	9
2.0 ANALYSIS POPULATIONS.....	10
2.1 Intent-to-Treat Population	10
2.2 Per Protocol (PP) Population.....	10
3.0 INTERIM ANALYSES.....	10
4.0 MISSING DATA AND DATA TRANSFORMATION	10
5.0 STATISTICAL METHODS	10
5.1 Protocol Deviations and Protocol Violations.....	11
5.2 Demographic and Baseline Characteristics.....	11
6.0 EFFICACY ANALYSIS.....	11
6.1.1 Primary Outcome	11
6.1.2 Statistical Hypothesis.....	12
6.1.3 Primary Efficacy Analysis.....	12
6.2 Secondary Efficacy Analyses.....	12

LIST OF TABLES

	Page
Table 1. Schedule of Assessments.....	8

LIST OF ABBREVIATIONS

AE	Adverse Event
AIS	Acute Ischemic Stroke
ANCOVA	Analysis of Covariance
CI	Confidence Interval
ECG	Electrocardiogram
EMS	Emergency Medical Services
e-CRF	Electronic Case Report Form
ICH	Intracerebral Hemorrhage
IQR	interquartile range
mRS	Modified Rankin Scale
NCCT	Non-contrast Computed Tomography Scan
NIHSS	National Institutes of Health Stroke Scale
PERDIEM	Post-Embolic Rhythm Detection with Implantable versus External Monitoring (PER DIEM) Study
PP	Per Protocol
SAE	Serious Adverse Event

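### Secondary outcome 3 counts AF/flutter from 30 seconds, but the implantable recorder stores only episodes of 2 minutes or longer

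*SAP*

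**What the plan says.** Protocol section 4.0 (Secondary Outcomes, item 3) and SAP section 6.1.1 (item 3) both list "Time to detection of first episode of atrial fibrillation / atrial flutter", with a threshold of 30 seconds or more. The item applies to both arms without distinction.

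The device adjudication instructions attached to the protocol, under ILR Device Capabilities/Troubleshooting, state: "Shortest duration of AF that Reveal LINQ can store is 2 minutes" (item 1) and "For PER DIEM the LINQ device is programmed to store AF Episodes with a duration of 2 minutes and longer" (item 3). Footnote a to the protocol's summary of changes gives the same limit as the reason for the April 2016 change of primary endpoint: "The shortest time over which the LINQ device can make a reliable assessment for AF is 2 minutes". The SAP clarification note records the amended primary endpoint as "definite AF lasting 2 minutes or more, including atrial flutter" and does not mention the secondary outcomes.

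For the comparator, Protocol section 3.3 says only: "The ELR group will be fitted with a battery operated SpiderFlash-t (Sorin Group, USA) auto-triggered ELR". It gives no minimum episode duration for that device.

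**The concern.** The outcome threshold lies below what one of the two randomised devices can store. In the ILR arm, device data can supply only the time to a first episode of 2 minutes or more, yet the result would be reported under a 30-second label. The steering committee saw this limit and corrected the primary endpoint for it; the same reasoning was not carried to outcome 3, which entered the 2019 SAP unchanged.

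At stake is a like-for-like comparison. If the ELR records episodes of 30 seconds to under 2 minutes, the arms are scored on different definitions. That component would work against the ILR, most plainly in the first 30 days, when both arms are being monitored. Over 12 months the net direction is not known, because the ILR goes on monitoring after the ELR has stopped.

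**Working it through.** The plan states no figure for this outcome that could be reproduced. The check compares stated thresholds.

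**Inputs**
- Outcome threshold: 30 s (Protocol 4.0 item 3; SAP 6.1.1 item 3).
- Shortest AF episode the ILR stores, and its programming in this trial: 2 min = 120 s (device instructions, items 1 and 3).
- Shortest ELR-detectable episode: not stated.
- Monitoring: ILR 12 months, ELR 30 days; 300 patients allocated 1:1 (Protocol 3.3).

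**Step 1: the gap.** Ratio of storage floor to outcome threshold = 120 / 30 = 4. Width of the unobservable band = 120 − 30 = 90 s. An episode lasting 30 s or more but less than 120 s satisfies the definition and is not stored by the ILR.

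**Step 2: what the ILR arm then measures.** A patient's first episode of at least 30 s cannot come later than the first episode of at least 120 s. The ILR records only the latter. A patient with a short episode followed by a long one gets a later time; a patient with only short episodes has no device-detected event.

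**Step 3: whether another part of the plan fills the gap.**
- Setting the device to store all episodes does not help. Item 3 gives that setting alongside the 2-minute floor, and item 1 says nothing shorter can be stored.
- Scheduled ECGs at Day 30 and 6 months (Protocol Appendix I) are snapshots. They, or a clinical diagnosis made elsewhere, may find some AF, but they cannot time the first 30-second episode.
- The SAP clarification note changes the primary endpoint only.

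**Step 4: scale.** Patients per arm = 300 / 2 = 150. Let k be the number of ELR patients who count only through an episode in the band. The documents do not give k, so the values below are assumptions for scale. The shift in the ELR detected proportion is k / 150:

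| k | Shift, percentage points |
|---|---|
| 0 (ELR does not capture such episodes) | 0 |
| 1 | 0.67 |
| 3 | 2.0 |
| 5 | 3.3 |

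The 10% and 20% rates in the sample size section are for arrhythmia that leads to a change in therapy, not for AF of 30 s or more. They are therefore not used to project a result for this outcome.

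**The case against.** The strongest reply is that the outcome is time to detection, not time to occurrence, and that the trial compares monitoring strategies. On that reading a device's sensitivity floor belongs to its strategy, just as 30 days versus 12 months does. Every stored ILR episode also exceeds 30 seconds, so a detection time exists in both arms. This has force as a description of what is compared, but it does not rescue the definition: the ILR result would still be a 2-minute outcome carrying a 30-second label, and the SAP does not say so.

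Other points stand in part:
- The between-arm bias depends on the ELR's minimum, which is not given. That is right, and no size is claimed; the ILR-arm problem does not depend on it.
- This is one secondary outcome in a pilot, and how formally it will be compared is unclear. SAP 5.0 says the primary outcome and the first composite "will be analysed by intention to treat, using time-to-event analysis" and leaves other secondary outcomes to proportions, while SAP 6.2 adds time-to-event analysis of the secondary outcome. This limits the importance of the point, not its validity.
- The written adjudication process covers only the ILR. However, the amended primary endpoint already requires definite AF of 2 minutes or more in both arms, so a 2-minute outcome 3 asks for nothing further.
- Device instructions item 6 warns that AF events under 10 minutes may arrive without data from devices purchased before March 7, 2016. The same item asks for a manual transmission in that case. The same issue would affect the primary endpoint.

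**Conclusion.** The concern holds. As written, outcome 3 cannot be ascertained from device data in the ILR arm for episodes of 30 seconds to under 2 minutes. This follows from the documents' own statements and rests on no power or rate assumption.

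The size and net direction of any effect on the comparison are unknown. It is zero if the ELR does not capture such episodes; otherwise each affected ELR patient moves that arm's proportion by 0.67 points. The primary comparison, on the amended 2-minute endpoint, is not affected. This should be corrected, but it does not threaten the trial's main conclusion.

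**What to change.** In Protocol section 4.0 and SAP section 6.1.1, redefine outcome 3 as the time to the first adjudicated episode of AF/flutter lasting 2 minutes or more, in both arms. Report episodes of 30 seconds to under 2 minutes descriptively, for the ELR arm only, and state the ELR's minimum detectable duration.

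If the 30-second wording is kept, the lesser option is to state that the outcome is not ascertainable below 2 minutes in the ILR arm and to make no between-arm comparison on it.

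As an optional addition, apply the same 2-minute floor to outcome 5, "Total duration of any detected atrial fibrillation / atrial flutter", so that durations are counted alike. This would drop any shorter ELR episodes and would not remove the difference between 30 days and 12 months of observation.

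The cost is a wording change, with no data beyond what the amended primary endpoint already needs. There are two downsides: results compare less directly with studies using a 30-second threshold, and a 2-minute outcome 3 would largely overlap the planned time-to-event analysis of the amended primary endpoint.

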6.1.2 Statistical Hypothesis

The primary hypothesis is: the rate of the primary outcome is 2-fold or more greater in the ILR group compared to the ELR group at 1 year (HR > 2.0)

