6.1.3 Primary Efficacy Analysis

Two sample comparison of proportions or patients reaching the primary outcome at one year, unadjusted.

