6.2 Secondary Efficacy Analyses

Two sample comparison of proportions or patients reaching the secondary outcome at one year, unadjusted.

Time to event analysis on the primary and secondary outcome.

Safety analyses by proportion of adverse events.

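### SAP 6.1.2 states the primary hypothesis as at least a doubling (HR > 2.0), but the planned primary test is of equal proportions and neither tests for a doubling nor gives a hazard ratio

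*SAP*

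**What the plan says.** - **Hypothesis (SAP 6.1.2):** "primary outcome is 2-fold or more greater in the ILR group compared to the ELR group at 1 year (HR > 2.0". This is the SAP's only formal statement of a hypothesis, and no null is given.
- **Primary analysis (SAP 6.1.3):** "Two sample comparison of proportions or patients reaching the primary outcome at one year, unadjusted". No null ratio, margin or named test is given.
- **Sample size (SAP 1.4, repeated from Protocol 5.0):** two-sided alpha of 5%, based on the "Two Independent Proportions (Null Case) Power Analysis estimation method (PASS 2012". The assumptions are 10% in the ELR arm "and 20% rate of this endpoint in the ILR plus remote monitoring group".
- **Objective (SAP 1.2):** ILR is expected to find more AF, "resulting in a greater proportion of patients started on an OAC". No 2-fold threshold appears there or in Protocol 2.1.
- **Time-to-event analysis:** SAP 5.0 says the primary outcome "will be analysed by intention to treat, using time-to-event analysis". SAP 6.2 lists "Time to event analysis on the primary and secondary outcome" among the secondary analyses. Neither names a model, a null hazard ratio or a threshold of 2.

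**The concern.** A doubling enters the design only as the effect assumed in 1.4. Section 6.1.2 turns that assumption into the hypothesis to be confirmed. The 6.1.3 comparison can show that the two proportions differ. It cannot show that one is at least twice the other.

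The p-value and the estimates do not depend on how 6.1.2 is worded. What is at stake is the claim: under the present wording, a significant result in 6.1.3 can be written up as confirming a primary hypothesis of at least a 2-fold rate.

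There are two further faults. A 2-fold ratio of proportions and a hazard ratio of 2 are different thresholds, yet 6.1.2 treats them as one. And a reader who looks for the analysis that would judge the hazard ratio finds it primary in 5.0 and secondary in 6.2.

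**Working it through.** **Inputs.** From SAP 1.4: 300 patients, 1:1, so n = 150 per arm; ELR 10%, ILR 20%; two-sided 5%; 8% allowance for cross-over and loss, so 300 × 0.92 / 2 = 138 per arm. True ratios of 1.5 and 1.8 are assumptions chosen to lie below 2.

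**1. The plan's own figures.** 20% / 10% = 2.0, so the 2-fold figure is exactly the design alternative. The stated 85% power does not reproduce. With pooled variance, z = (0.10·√150 − 1.96·√(2·0.15·0.85)) / √(0.09 + 0.16) = 0.470, so power is about 68% (exact enumeration 68.6%). That is a separate issue and this point does not depend on it.

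**2. Two-fold versus HR 2.0.** Under proportional hazards, HR = ln(1 − p_ILR) / ln(1 − p_ELR).
- 10% versus 20%: ln 0.8 / ln 0.9 = 2.12.
- HR 2.0 with ELR 10%: p_ILR = 1 − 0.9² = 19%, a risk ratio of 1.90.

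**3. How often the 6.1.3 test is significant when there is no doubling, or none is observed.** Exact binomial enumeration, ELR 10%, two-sided p < 0.05 with ILR higher:

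| True ILR rate (ratio) | n per arm | Event | Uncorrected chi-square | Fisher |
|---|---|---|---|---|
| 15% (1.5) | 150 | significant | 25.7% | 20.9% |
| 18% (1.8) | 150 | significant | 51.7% | 45.6% |
| 20% (2.0) | 150 | significant, observed ratio below 2 | 15.7% | 10.3% |
| 20% (2.0) | 138 | significant, observed ratio below 2 | 12.3% | 7.2% |

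**4. Examples with 15/150 in the ELR arm.** 95% CI for the risk ratio: exp[ln RR ± 1.96·SE], SE = √(1/x − 1/n + 1/y − 1/n), with x ELR events and y ILR events.
- y = 27: RR 1.80; p = 0.046 uncorrected, 0.067 corrected, 0.066 Fisher. The verdict depends on a test that the SAP does not name.
- y = 28: RR 1.87; SE = √(0.0667 + 0.0357 − 0.0133) = 0.298; CI 1.04 to 3.35; p = 0.032, 0.048 and 0.047. All three tests are significant, with an observed ratio below 2.
- y = 30: RR 2.00; CI 1.12 to 3.56. Even an observed doubling does not establish a true one.
- y = 50: lower limit 1.96. y = 51: lower limit 2.003, RR 3.40. This is the smallest ILR count that puts the lower limit above 2.

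**5. A test that matches 6.1.2.** If the null is a ratio of 2 or less, the planning rates lie on its boundary, so the chance of rejection is close to the test's alpha. A Wald test of p_ILR − 2·p_ELR at one-sided 2.5%, with 150 per arm, rejects in 3.6% of trials (exact). The trial could hardly ever confirm 6.1.2 when its own planning assumption is true.

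**The case against.** The strongest reply is that 6.1.2 only records the effect the investigators expect. On that reading it is a loosely drafted alternative hypothesis, and 1.2 and 1.4 show that equality was always the null. The 26% and 52% are then just the power of the equality test at ratios 1.5 and 1.8, and they become false declarations of doubling only under a claim rule that the SAP does not state. Many of those significant trials would also show an observed ratio of 2 or more: with the uncorrected test, only 5.6% (true ratio 1.5) and 12.5% (true ratio 1.8) of trials are significant with an observed ratio below 2. SAP 5.0 plans 95% confidence intervals in general, the protocol presents the trial as a feasibility pilot, and the gap between HR 2.0 and 2.12 is small.

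Much of this stands. The percentages are conditional, the 6.1.3 test is unaffected, and the hazard-ratio gap matters as labelling more than as a number. The reply does not remove the mismatch. An expected effect belongs in 1.4, where it already is; under a heading for the statistical hypothesis it defines what a positive trial has shown. Section 5.0 does not tie the 2-fold statement to a confidence limit, and the SAP's own sample-size section does not call the trial a pilot. The conflict over which analysis is primary would remain even if 6.1.2 were deleted, but it has to be settled in the same edit because 6.1.2 invokes a hazard ratio.

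**Conclusion.** The concern holds and should be fixed; it is a fault of wording and claim, not of the test itself. The stated primary hypothesis is not what the primary analysis examines, no planned test has a null ratio of 2, and 5.0 and 6.1.3 disagree on whether time-to-event analysis or a comparison of proportions is primary.

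If significance in 6.1.3 is taken to confirm 6.1.2, a doubling would be declared in about 21% to 26% of trials at a true ratio of 1.5, and in 46% to 52% at 1.8, depending on the test. These figures assume 150 per arm with complete data and a 10% ELR rate. The hazard-ratio conversion assumes proportional hazards. The text mismatch rests on none of these assumptions.

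**What to change.** **Option A, which matches 1.2, 1.4, 6.1.3 and 6.2.**
- **6.1.2:** replace with *H0: the one-year proportions with the primary outcome are equal in the two groups; H1: they differ; two-sided alpha 5%. A doubling (10% versus 20%, section 1.4) is the planning assumption and is not what the test establishes.* Delete the hazard-ratio label.
- **6.1.3:** name the test, and report the risk difference and risk ratio with 95% CIs.
- **5.0:** say that the primary outcome is compared by intention to treat as one-year proportions, and that time-to-event analyses of it and of the first composite secondary outcome are secondary, as in 6.2.

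**Option B, if the sponsor wants to keep a claim of at least 2-fold.** Make the Option A edits and add that the claim is made only if the lower 95% limit of the one-year risk ratio exceeds 2. State that the trial is not sized for this: with 15/150 in the ELR arm it needs at least 51/150 in the ILR arm.

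**Cost.** Either option is a dated SAP amendment to three sections, with no new data and no change to trial conduct. Under A the trial may claim superiority only. Under B the 2-fold claim survives but is unlikely to be met at this sample size. The 85% power figure and the superseded endpoint noted at the front of the SAP need separate handling.
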